1 INTRODUCTION

Myopia is a significant public health problem, it has been predicted that by 2050, 50% of the world population will be myopic. (1) Myopia can be defined as an eye that is excessively long and with the increase in axial length comes an increased risk of developing ocular pathology. This increased risk is directly related to the amount of myopia, individuals with high myopia being as much as 40x more likely to have pathology that can result in loss of vision compared to individuals with low amounts of myopia.(2) There is very good evidence in the literature that there are interventions that can slow down the progression of myopia and hence reduce the risk of ocular pathology. One such intervention is the MiSight contact lens. In a three year study, the MiSight lens reduced the myopic progression of a group of subjects by 59% compared with their control group counterparts.(3) Subjects for the original MiSight study were aged 8-12 at recruitment, this being a typical age group when myopia is first seen. There is a cohort of patients who experience later onset of myopia and progression into early adult hood. The COMET study demonstrated that on average, myopia stabilizes by age 15 (48%), however, 90% of the cohort had stable myopia by age 21 and 96% by age 24.(4) Therefore it is clear that there is a proportion of the population whose myopic prescription continues to progress into early adulthood. To date there is no evidence in the literature that commencing a myopia control program in young adult myopes would have an impact on the progression of their myopia. The purpose of this study is to assess whether young adults can adapt to and achieve satisfaction with the MiSight lens. The results from this short term study may contribute towards the planning for longer term studies for the same population sample.

2 OBJECTIVES

The objectives of the study are:

- To measure objective and subjective visual performance, patient satisfaction and to determine if these aspects change over time as myopic young adults adapt to MiSight soft contact lenses.

Primary outcome variable:

- Subjective quality of vision (QoV)

Secondary outcome variable:

- Contact lens Impact on Quality of Life (CLIQ)

[REDACTED]

[REDACTED]

[REDACTED]

[REDACTED]

[REDACTED]

[REDACTED]

[REDACTED]

[REDACTED]

3 HYPOTHESIS

Young adults will achieve good subjective quality of vision (QoV) scores with the MiSight lenses.

4 MATERIALS AND METHODS

4.1 STUDY DESIGN

4.1.1 OVERALL DESIGN

This is a prospective, single group, dispensing clinical trial to determine subjective and objective visual performance measures, patient satisfaction and adaptability to commercially available myopia control contact lenses (MiSight 1-day) in myopic young adults over 3 months of daily lens wear. There will be 4 scheduled in-office sessions and one remote/at home session spanning a total commitment time of 5.5 hours over the 3 months. The first session is anticipated to include the screening visit, visit 1 (V1) and, if eligible, visit 2 (V2) will be conducted in immediate succession. Visit 2 may be conducted on a separate day if necessary, but should be scheduled within 10 days of visit 1.

- **Visit 1 (V1):** Screening and Baseline (75 mins)
- **Visit 2 (V2):** Fitting/Dispensing of study lenses (15 mins if immediately following V1 on the same day)
Note – V2 can take place on a separate day, if necessary, but should be scheduled within 10 days of V1. Entrance acuity and biomicroscopy will be required in this case, and time required would be increased to 30 minutes.
- **Visit 3 (V3):** Day 7, Follow-up (60 mins)

- **Visit 4 (V4):** 1 month, Follow-up (75 mins)
- **Visit 5 (V5):** 2 month, Remote at home questionnaires (15 mins)
- **Visit 6 (V6):** 3 month, Follow up and exit (90 mins)

4.1.2 MASKING

This is an open-label study that will not involve masking.

4.2 STUDY POPULATION

4.2.1 SAMPLE SIZE CALCULATION

Using a conservative estimate for repeated measure ANOVA paradigm, with 1 group, with 3 measurements (baseline, 1 month, 2 months) and f effect size of 0.25 (cumulative probability 75%), and 1-beta 0.95, the minimum sample size is n = 43. Using an attributed drop-out rate of 10-15%, the required sample size to be dispensed will be 50 participants.

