4.2.2 NUMBER OF PARTICIPANTS

Participants will be recruited using CORE database and advertising approved by the UW Office of Research Ethics. Up to 50 participants who meet all eligibility criteria may be dispensed with MiSight study lenses and asked to wear these lenses for 3 months (\pm 7 days), with a target of 43 completing the study. Participants who were screened but did not meet all eligibility criteria are not included in the number of participants (n=50) to be dispensed. Informed consent will be obtained for all participants prior to their enrolment in the study and prior to collecting any study data (Appendix 1).

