4.4.2 VISIT 1, SCREENING

A documented informed consent process will be conducted with all participants prior to their enrolment in the study and prior to any data collection or measurements.

Participants will be assigned a study ID number after they sign the consent documentation process i.e. before their eligibility for the study has been confirmed. The investigator will determine participant eligibility using the inclusion and exclusion criteria. Ineligible participants will be discontinued from the study. The procedures to be performed are outlined below:

1. Informed consent
2. Participant demographics and medical history:
 - *Age, Sex*
 - *Medical history/medications, Allergies*
3. CL wear history
 - *Habitual contact lens wear (CL type, cleaning solution (if applicable), wear time)*
4. Subjective questionnaires (QoV and CLIQ) with habitual lenses within the last month of lens wear experience
5. Presenting visual acuity
6. Auto refraction/auto keratometry
7. Sphero-cylindrical refraction, monocular & binocular logMAR distance HIHC VA

13. Slit lamp biomicroscopy
14. MiSight study lens fitting
 - a. The contact lens power will be chosen based on the vertex best sphere refraction.
 - b. The participant will insert the lenses.

- c. Acceptability of lens fit (centration, movement, limbal coverage, overall; YES/NO) will be confirmed.
- d. Monocular over-refraction will be performed to determine if a different power is needed. If any changes are made, the above procedures will be repeated.
- e. The final lens powers for OD and OS and monocular & binocular logMAR distance HIHC VA will be recorded.

15. Confirm eligibility.

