4.4.4 VISIT 3, 2 WEEK FOLLOW-UP

Participant to attend visit after 2 hours or more of MiSight study lens wear.

1. Changes in medical history/medications;
2. Compliance with # of CL wear days/hours per day
3. Presenting VA

5. Spherical over-refraction
6. Slit lamp biomicroscopy
7. Questionnaires (CLIQ, QoV)
8. Lens removal

9. Biomicroscopy examination

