10 STATISTICAL ANALYSIS AND DATA MANAGEMENT

10.1 STATISTICAL ANALYSIS

All data will be analyzed by CORE at the University of Waterloo. Data analysis will be conducted using Statistica, SPSS, or other appropriate software.

Descriptive statistics will be provided for all primary outcome variables as well as information regarding baseline variables (e.g. age, sex).

QoV and CLIQ ratings will be compared between visits using either Paired t-tests or Wilcoxon matched pairs, or using ANOVA, as applicable; statistical significance will be set at 5%. The appropriate tests will be selected based on tests of normality - non-parametric tests will be used for data not showing a normal distribution. For assessments conducted for each eye separately, the right eye will be used for analysis if there is no difference between eyes.

Additional analysis may be conducted.

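### Section 4.2.1 powers three QoV visits ending at 2 months, but QoV is collected at five visits to 3 months, and 10.1 names no primary comparison or multiplicity rule

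*Combined protocol and SAP*

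**What the plan says.** Section 4.2.1 takes a one-group repeated-measures ANOVA as the basis for the sample size: "with 1 group, with 3 measurements (baseline, 1 month, 2 months) and f effect size of 0.25 (cumulative probability 75%), and 1-beta 0.95". This yields a minimum of 43, and 50 are to be dispensed to allow for drop-out. Section 4.2.2 applies the same 43 to the full period of wear: "with a target of 43 completing the study". Section 4.1.1 describes follow-up "in myopic young adults over 3 months of daily lens wear".

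QoV is the primary outcome in section 2, with no time point attached. Sections 4.4.2 and 4.4.4 to 4.4.7 schedule it five times:

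- V1, for the habitual lenses: "Subjective questionnaires (QoV and CLIQ) with habitual lenses within the last month of lens wear experience"
- V3 (2 weeks), V4 (1 month), V5 (2 months, remote) and V6 (3 months), all in study lenses

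Table 3 may add a collection at a separate dispensing visit; the counts below use the five scheduled visits. Section 4.1.1 puts V3 at day 7 and Table 2 at day 14. Those sections must be reconciled, but the count of five does not change.

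The objective is "to determine if these aspects change over time as myopic young adults adapt to MiSight soft contact lenses". Section 10.1 compares ratings between visits "using either Paired t-tests or Wilcoxon matched pairs, or using ANOVA, as applicable; statistical significance will be set at 5" per cent, with the test chosen after normality checks. Nothing in the document names a primary contrast, a testing order or an adjustment for multiple tests.

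**The concern.** The test that was powered is not tied to the test that will be run. The stated 95% power describes a set of visits that omits V3 and the 3-month visit, while 10.1 leaves the choice among several tests, and among up to ten pairs of visits, until the data are in.

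Two things are at stake. First, unadjusted pairwise testing can produce a false finding that QoV changes, which is the question the objective asks. Second, the baseline rating is for a different lens. A difference from baseline may reflect the switch of lens and not adaptation to MiSight, so an overall visit effect does not by itself answer the adaptation question, and it gives weak protection to tests made after it.

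**Working it through.** **Inputs.** From 4.2.1: m = 3 measurements, f = 0.25, power 0.95, n = 43. From 10.1: alpha 0.05. Not stated, so assumed: correlation rho between visits (0.5, with 0.3 and 0.7 as a range) and sphericity epsilon (1, with 0.75 as an alternative).

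**Reproducing 43.** Noncentral F with lambda = n·m·f²·eps/(1 − rho), df1 = (m − 1)·eps and df2 = (n − 1)(m − 1)·eps. For n = 43, lambda = 43 × 3 × 0.0625/0.5 = 16.125 on 2 and 84 df, and power is 0.951. With n = 42 it is 0.947, so the minimum is 43, as stated. The result depends on the assumed correlation: at n = 43, power is 0.856 for rho 0.3 and 0.997 for rho 0.7.

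**Five visits, same f.** lambda = 43 × 5 × 0.0625/0.5 = 26.875 on 4 and 168 df; power is 0.992.

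**Five visits, size of the change held fixed.** f is the SD of the visit means in units of the within-visit SD, so the same change can give a different f when visits are added. Each pattern below is scaled to f = 0.25 over baseline, 1 month and 2 months (three-visit power 95.1% at rho 0.5, 85.6% at rho 0.3).

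- Pure baseline shift d: f = d·√(m − 1)/m. At m = 3, d = 0.25 × 3/√2 = 0.53 SD. At m = 5, f = 0.53 × 2/5 = 0.212.
- Two visits at the extremes, the rest midway: f = d/√(2m). At m = 3, d = 0.25 × √6 = 0.61 SD. At m = 5, f = 0.61/√10 = 0.194.

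| Pattern | Five-visit f | Power, rho 0.5 | Power, rho 0.3 |
|---|---|---|---|
| Baseline shift | 0.212 | 95% | 85% |
| Baseline shift, epsilon 0.75 | 0.212 | 90% | 76% |
| Two extremes, rest midway | 0.194 | 91% | 77% |
| Linear by visit | 0.283 | 99.9% | 98.6% |
| Shift after 2 weeks, or at 2 months, then held | 0.260 | 99.5% | 96.5% |
| Gradual in calendar time, plateau from 2 months | 0.245 | 99.0% | 94.2% |

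So five-visit power can be higher or lower than the three-visit figure.

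**False-positive rates, no true change.** Simulation with n = 43, normal equally correlated data, 40,000 runs, unadjusted paired t-tests at 5%, counting runs with at least one significant pair:

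| Pairs tested | Rate |
|---|---|
| Four against baseline | about 15% |
| Six among V3 to V6 | about 21% |
| All ten pairs of the five visits | about 29% |

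These hardly move for rho between 0.3 and 0.7. The five-visit ANOVA alone gives 5% under the same equal correlations. Without a sphericity correction it gives about 7% to 8% if the habitual-lens baseline correlates 0.3 with follow-up and the follow-up visits correlate 0.7 to 0.8 with each other (assumed values).

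**Lens switch without adaptation.** Shift the baseline by 0.53 SD and keep V3 to V6 equal. The ANOVA is then significant in about 95% of runs (the power above). Unadjusted tests among V3 to V6 after a significant ANOVA give a false adaptation result in about 20% of runs.

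**The case against.** The strongest reply is that the power complaint changes almost no number. The calculation uses how many measurements there are, not which ones. The arithmetic is correct, 4.2.1 calls its estimate conservative, and at the same f and correlation five visits would need only 31 participants. That stands. A reader might infer from the missing 3-month visit that 43 is wrong or too few, or that adding visits lowers power. The documents support neither: the usual linear, delayed and plateau patterns gain power.

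A second reply is that 4.2.1 names an ANOVA and 10.1 lists one, so 15% to 29% is not a planned error rate. That is also fair. The figures apply only if the pairwise route is taken, left unadjusted, and any significant pair is called change. They also assume normal data, whereas 10.1 turns to Wilcoxon tests otherwise. But 10.1 does not commit to ANOVA, and ANOVA is not a full answer. It holds 5% only under sphericity, which is doubtful when one rating is for a different lens, and it does not protect the adaptation comparisons once the lens switch has made it significant.

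Third, this is a single-group, open-label study of a marketed lens, meant to help plan longer studies, and formal multiplicity control is partly a matter of preference. This bears on how serious the point is. It does not remove the need to say which QoV comparison answers the objective.

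**Conclusion.** The point holds as an unspecified primary analysis with a misaligned power statement, and should be fixed. The three-visit basis and the five scheduled collections are plain in the text, as is the absence of any primary comparison or multiplicity rule in 10.1.

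The size of the problem is conditional. The unadjusted pairwise route carries about 15%, 21% or 29% risk of a false QoV change, depending on the pairs tested. A lens-switch effect of 0.53 SD followed by unadjusted tests carries about 20% risk of a false adaptation result. Both rest on normal, equally correlated data with 43 completers. The trial is not shown to be too small, and these rates are not what the sponsor has committed to.

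The hypothesis in section 3, "Young adults will achieve good subjective quality of vision (QoV) scores with the MiSight lenses", is a separate question: no between-visit test addresses whether scores are good.

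**What to change.** **In 10.1**, name one primary QoV analysis at 5% that includes the 3-month visit, for example the visit effect in a five-visit repeated-measures model with a sphericity correction. Only after a significant visit effect, run follow-up tests in two families, Holm-adjusted within each: four against the habitual-lens baseline (lens switch) and six among V3 to V6 (adaptation). If adaptation alone is to be primary, use the visit effect over the four study-lens visits. One visit differing by 0.53 SD then gives f = 0.53 × √3/4 = 0.230, with power about 95% at correlation 0.5 and 86% at 0.3.

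**In 4.2.1**, keep 50 dispensed and 43 completers, replace the three-visit description with the chosen analysis, and state alpha, correlation and sphericity. Suggested wording: five visits, n = 43, alpha 0.05, baseline shift 0.53 SD (f = 0.212): power 95% at correlation 0.5 and 85% at 0.3; with epsilon 0.75, 90% and 76%.

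**Cost.** Wording only, with no extra participants. A paired test at 0.53 SD of the paired difference has about 92% power at 5%. At Holm's strictest step this falls to 80% for four comparisons (0.05/4 = 0.0125) or 76% for six (0.05/6 = 0.0083). In the simulated patterns (equal correlations) each family stayed under 5%, and the chance of a false result in either family reached about 8%.

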4.2.2 NUMBER OF PARTICIPANTS

Participants will be recruited using CORE database and advertising approved by the UW Office of Research Ethics. Up to 50 participants who meet all eligibility criteria may be dispensed with MiSight study lenses and asked to wear these lenses for 3 months (\pm 7 days), with a target of 43 completing the study. Participants who were screened but did not meet all eligibility criteria are not included in the number of participants (n=50) to be dispensed. Informed consent will be obtained for all participants prior to their enrolment in the study and prior to collecting any study data (Appendix 1).

4.2.3 INCLUSION AND EXCLUSION CRITERIA

A person is eligible for inclusion in the study if he/she:

1. Is between 17 and 25 years of age (inclusive) and has full legal capacity to volunteer;
2. Has read and signed an information consent letter;
3. Is willing and able to follow instructions and maintain the appointment schedule;
4. Has a vertex corrected spherical equivalent distance refraction that ranges between -0.75D to -6.00D in each eye;
5. Has astigmatism \leq -0.75 DC in either eye, by refraction;
6. Be correctable to better than 0.20 logMAR in each eye by refraction;
7. Has habitually worn spherical soft contact lenses to correct for distance vision (i.e. no multifocal or monovision) for the past 3 months;

8. Is willing to wear contact lenses for at least 10 hours a day, 6 days a week while in the study;
9. Demonstrates an acceptable fit with the study lenses;
10. Has ocular health findings considered to be “normal” and which would not prevent the participant from safely wearing contact lenses.

A person will be excluded from the study if he/she:

1. Is participating in any concurrent clinical or research study;
2. Has a history of amblyopia;
3. Has TNO Stereoacuity worse than 120" arc / or Titmus worse than 100" arc;
4. Has any known active* ocular disease and/or infection;
5. Has a systemic condition that in the opinion of the investigator may affect a study outcome variable;
6. Is using any systemic or topical medications that in the opinion of the investigator may affect a study outcome variable;
7. Has known sensitivity to the diagnostic pharmaceutical (sodium fluorescein) to be used in the study;
8. Is pregnant, lactating or planning a pregnancy at the time of enrolment (verbal confirmation at the screening visit);
9. Is pseudophakic;
10. Has undergone refractive error surgery;
11. Has one of following experiences with MiSight lenses:
 - Is currently wearing MiSight lenses or
 - Has worn MiSight lenses for more than one week at any given time or
 - Has worn MiSight lenses for any more than 30 minutes in the past 30 days;
12. Has had orthokeratology treatment within the last 3 months.

* For the purposes of this study, active ocular disease is defined as infection or inflammation, which requires therapeutic treatment. Mild (i.e. not considered clinically relevant) lid abnormalities (blepharitis, meibomian gland dysfunction, papillae), corneal and conjunctival staining and dry eye are not considered active ocular disease. Neovascularization and corneal scars are the result of previous hypoxia, infection or inflammation and are therefore not active.

Pregnant and lactating women are not being excluded from the study due to safety concerns but due to changes in physiology that occur secondary to systemic hormonal changes which may impact refractive error and visual acuity.

4.2.4 REPEATED SCREENINGS

In some circumstances a repeated screening may need to be scheduled (Visit 1-R). Examples include, but are not limited to:

1. Incomplete information available at time of screening to determine eligibility (e.g. current lens brands worn, history from current eye care practitioner etc.)
2. Study procedures unable to be completed in time scheduled for visit;
3. Study products not available at the time of the screening visit;
4. A transient health condition which may affect the eye(s) (e.g. a common cold, active allergies, fatigue etc;)
5. The short term use of medications (e.g. antibiotics, antihistamines etc.)
6. Reassessment of baseline ocular conditions (e.g. corneal and/or conjunctival staining, scars etc.)

The maximum total number of screenings permitted will be 3, i.e. 2 re-screen visits are permitted.

4.3 STUDY MATERIALS

4.3.1 LENSES

The study lenses are approved by Health Canada. They will be worn bilaterally, and on a daily disposable basis as per the approved indication, therefore no lens care solution is required.

Table 1: lens characteristics

Lens	MiSight
Material	Omafilcon A
HC licence #	83469
Medical device class	2
Dk/t (barrer/cm)	28
Water content	59%
Sphere power (D)	-0.50 to -6.00 (0.25 steps)
Base curve (mm)	8.7
Diameter	14.2
Replacement schedule	Daily disposable

4.3.2 ORDERING CONSUMABLES

MiSight study lenses will be supplied by CooperVision for the use in this study.

4.3.3 DISPOSING OF CONSUMABLES

Worn lenses removed during study visits will be discarded as per University of Waterloo regulations. Unworn lenses will be returned or disposed of, as advised by the sponsor, and according to University of Waterloo regulations.

4.3.4 PRODUCT ACCOUNTABILITY

Accountability logs will be kept to include the number of lenses received, dispensed, unused and, if required, returned to sponsor. All products dispensed to participants will be recorded in individual participant logs in the study binder.

4.4 SCHEDULED AND UNSCHEDULED VISITS

There will be four in-office study sessions, including a screening visit. Participants will attend the clinical site for a total of 5.25 hours and will also be asked to complete at home ratings after 2 months, to assess their experience with the study contact lenses.

4.4.1 STUDY VISITS

A summary of study visits is shown in Table 2.

Table 2: Summary of visits

	Visit #	Day/s	Visits	Duration (hours)
In-office session 1	Visit 1	0	Screening and fitting	1.25
	Visit 2	0	Baseline & Dispense.	0.25
In-office session 2	Visit 3	14 ± 4	2 week follow up	1.0
In-office session 3	Visit 4	28 ± 7	1 month follow up	1.25
At-home session 1	Visit 5 – Virtual visit	56 ± 7	2 month at-home questionnaires	0.25
In-office session 4	Visit 6 & Exit	84 ± 7	3 month follow up and exit	1.5

Visits that fall outside of the specified visit windows will be designated as minor protocol deviations and at the end of the study, the data collected during protocol deviations will be assessed for their suitability to be included in the analysis population.

4.4.2 VISIT 1, SCREENING

A documented informed consent process will be conducted with all participants prior to their enrolment in the study and prior to any data collection or measurements.

Participants will be assigned a study ID number after they sign the consent documentation process i.e. before their eligibility for the study has been confirmed. The investigator will determine participant eligibility using the inclusion and exclusion criteria. Ineligible participants will be discontinued from the study. The procedures to be performed are outlined below:

1. Informed consent
2. Participant demographics and medical history:
 - *Age, Sex*
 - *Medical history/medications, Allergies*
3. CL wear history
 - *Habitual contact lens wear (CL type, cleaning solution (if applicable), wear time)*
4. Subjective questionnaires (QoV and CLIQ) with habitual lenses within the last month of lens wear experience
5. Presenting visual acuity
6. Auto refraction/auto keratometry
7. Sphero-cylindrical refraction, monocular & binocular logMAR distance HIHC VA

13. Slit lamp biomicroscopy
14. MiSight study lens fitting
 - a. The contact lens power will be chosen based on the vertex best sphere refraction.
 - b. The participant will insert the lenses.

- c. Acceptability of lens fit (centration, movement, limbal coverage, overall; YES/NO) will be confirmed.
- d. Monocular over-refraction will be performed to determine if a different power is needed. If any changes are made, the above procedures will be repeated.
- e. The final lens powers for OD and OS and monocular & binocular logMAR distance HIHC VA will be recorded.

15. Confirm eligibility.

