4.4.3 VISIT 2, BASELINE & DISPENSE (DAY 0)

Participants who successfully met all eligibility criteria in Visit 1 will directly transition to Visit 2, while continuing to wear the pair of study lenses that has just been fitted.

1. Lens dispense: Participants will be provided with a supply of MiSight CLs to last them for the period of the study.
2. Participant instructions. The participants will be asked to:
 - *Wear the lenses at least 6 days per week and 10 hours per day throughout the study;*
 - *Attend V3 after 2 hours or more of MiSight study lens wear on that day;*

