4.5.1 CASE HISTORY

Demographics:

Demographic information from the participant will be obtained, including age and sex.

Medical History:

At screening, information will be obtained from participants about the current medication, allergies, and any medical conditions. At visits 2 (if applicable), 3, 4 and 6 participants will be asked about changes in their medication or health.

Contact Lens History:

Information will be obtained from the participant about the current contact lens type (lens name, brand), lens power and use of artificial tears. Participants will be asked their typical lens wear time (hours/day and days/week).

4.5.2 QUALITY OF LIFE (CLIQ) AND QUALITY OF VISION QUESTIONNAIRES (QOV):

Participants will be asked to complete questionnaires based on the time period of contact lens wear specified in the questionnaire.

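### The baseline-versus-MiSight contrast in QoV and CLIQ mixes lens design with a prescription update, because habitual lens power need not match the current refraction

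*Combined protocol and SAP*

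**What the plan says.** **Baseline rating.** Section 4.4.2, item 4, has participants complete "Subjective questionnaires (QoV and CLIQ) with habitual lenses within the last month of lens wear experience". This comes before the refraction (items 6 and 7) and before MiSight fitting (item 14). A footnote to Table 3 in 4.5 confirms that the screening questionnaires refer to habitual lenses.

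**Rules on the habitual lenses.** Inclusion 7 in 4.2.3 reads "Has habitually worn spherical soft contact lenses to correct for distance vision (i.e. no multifocal or monovision) for the past 3 months". The acuity criterion, inclusion 6, is "Be correctable to better than 0.20 logMAR in each eye by refraction", so it does not test acuity through the habitual lenses. No visible criterion covers the power of those lenses, the age of the prescription, or a minimum wearing time.

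**MiSight power and wear.** Under item 14 of 4.4.2, "The contact lens power will be chosen based on the vertex best sphere refraction", and then "Monocular over-refraction will be performed to determine if a different power is needed". In 4.4.3 participants are asked to "Wear the lenses at least 6 days per week and 10 hours per day throughout the study".

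**Data recorded.** Section 4.5.1 states: "Information will be obtained from the participant about the current contact lens type (lens name, brand), lens power and use of artificial tears". It also records typical habitual wearing time.

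**Analysis.** Section 4.2.1 counts baseline as one of three repeated measurements. Section 10.1 compares QoV and CLIQ between visits by paired tests or ANOVA, with no covariate or sensitivity analysis for habitual lens power or wear.

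**The concern.** There is one group and no concurrent control, so the participant's own baseline is the only reference for a comparison with ordinary lenses. Two things change between that baseline and the first MiSight rating: the lens design and, for anyone whose habitual lenses are out of date, the refractive correction.

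Under-correction would make the baseline rating worse than it would have been in up-to-date single-vision lenses. The change to MiSight would then look more favourable than its optics warrant, and a real loss of visual quality on the primary outcome could be reported as no change. The Introduction says the results may inform longer studies in the same population, so such a result could be carried forward.

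Wearing time may change at the same point, because no habitual minimum is set and the study asks for 6 × 10 = 60 hours a week. That difference also enters the contrast, but the documents do not show which way it acts.

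**Working it through.** **Inputs from the documents.** f = 0.25, three measurements including baseline, power 0.95 and n = 43 (4.2.1); significance level 5% (10.1).

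**Assumptions, not in the documents.** Correlation between visits 0.5; sphericity; two-sided test; the share of participants with out-of-date lenses; the QoV cost to each. No SD for QoV is given, so everything is in SD units.

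**1. The plan's own figure.** For a one-group repeated-measures ANOVA, λ = f²·n·m/(1 − ρ), with m − 1 and (n − 1)(m − 1) degrees of freedom. With n = 43, m = 3 and ρ = 0.5, λ = 0.0625 × 43 × 3 / 0.5 = 16.1 on 2 and 84 df, and power is 0.951. The smallest n reaching 0.95 is 43, so the stated figure is reproduced.

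**2. What f = 0.25 means for this contrast.** Suppose baseline differs by d SD from two equal MiSight visits. The SD of the three means is d·√2/3, so d = 0.25 × 3/√2 = 0.53 SD.

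**3. Bias.** If a share p has out-of-date lenses and each loses c SD at baseline, the mean bias is b = p·c, and a true loss of 0.53 SD appears as 0.53 − b.

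**4. Power at n = 43.** The SD of a paired difference is √(2(1 − ρ)), which is 1 at ρ = 0.5, so the standardised paired difference is 0.53 − b. The calculation holds that SD fixed.

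| p | c | b (SD) | b/0.53 | Apparent loss (SD) | Paired t power | ANOVA power |
|---|---|---|---|---|---|---|
| 0 | – | 0 | 0% | 0.530 | 0.925 | 0.951 |
| 10% | 0.5 | 0.05 | 9% | 0.480 | 0.868 | 0.903 |
| 10% | 1.0 | 0.10 | 19% | 0.430 | 0.787 | 0.825 |
| 25% | 0.5 | 0.125 | 24% | 0.405 | 0.738 | 0.775 |
| 25% | 1.0 | 0.25 | 47% | 0.280 | 0.435 | 0.447 |

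At correlation 0.7 the paired SD is √0.6 = 0.775. Power is then higher throughout: for b = 0.125 and 0.25 it is 0.92 and 0.64.

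**5. Whether covariate adjustment removes the bias.** Regress the change on the habitual error e. With e centred at its mean, the fitted intercept is the raw mean change, so the bias remains. The change at zero error is (mean change) − slope × (mean error), and it is this quantity that takes out the prescription update.

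**The case against.** **The contrast is not the stated hypothesis.** Section 3 expects good QoV scores with MiSight, and section 2 asks about change during adaptation. Neither claims superiority or non-inferiority to habitual lenses. Ratings at 2 weeks and at 1, 2 and 3 months are all in MiSight and do not use the habitual rating. Moving from the lenses a patient actually wears is also a legitimate real-world comparison. This stands and limits the point to one contrast. It does not remove the point, because 4.2.1 and 10.1 put baseline among the compared visits.

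**Out-of-date lenses may be uncommon.** A reader might infer from the Introduction, with its interest in myopia that progresses into adulthood, that under-correction is to be expected here. The documents do not support that. Their own figures have myopia stable in 90% by age 21 and 96% by 24, enrolment covers ages 17 to 25, and progression is not required. Nor does progressing mean wearing an old prescription. Hence the range starting at 10%, which is itself an assumption.

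**Wear time.** A reader might also infer that heavier study wear helps to hide a loss. Lighter habitual wear could just as well improve the baseline rating and exaggerate a loss. The 60 hours is an instruction with compliance recorded, not a guaranteed exposure.

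**Hidden text.** Items 8 to 12 of Visit 1 and some Table 3 rows are not visible, so a check of the habitual lenses cannot be excluded. The visible over-refraction row shows none at screening, and 10.1 uses no such check.

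**Conclusion.** The point holds for the baseline-versus-MiSight contrast in QoV and CLIQ and for nothing else. As written, that contrast cannot separate lens design from a prescription update. Where habitual lenses are under-corrected, the bias favours MiSight. The effect of differing wear time has no determined direction.

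The size is conditional. With 10% to 25% affected at a cost of 0.5 to 1.0 SD each, the bias is 0.05 to 0.25 SD, or 9% to 47% of the 0.53 SD shift implied by f = 0.25. Paired power falls from 92% to between 87% and 44%. The share, the cost and the correlation of 0.5 are all assumed; a higher correlation softens the loss of power but leaves the bias itself unchanged. The documents do not show that a loss will be hidden, only that the planned analysis could not tell. The sample size of 43 needs no change on this account.

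**What to change.** Add to 10.1, as a prespecified sensitivity analysis of the baseline-to-MiSight change in QoV and CLIQ:

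1. **Derive the habitual residual error.** For each eye, take the vertex-corrected best-sphere refraction at Visit 1 minus the recorded habitual lens power. Use the larger absolute error of the two eyes as the person-level value, so that signed errors do not cancel.
2. **Regress the change on this error** and report the estimated change, with its confidence interval, at zero error and not at the mean error.
3. **Repeat the contrast** in participants whose habitual lenses fall within a prespecified tolerance, such as 0.25 D.
4. **Describe the contrast by habitual wearing time**, without a directional claim.

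Also state that habitual lens power is captured at Visit 1. Section 4.5.1 collects it, but item 3 of 4.4.2 names only lens type, cleaning solution and wearing time. Presenting acuity (item 5) set against refracted acuity (item 7) is a useful cross-check in those who arrive wearing their habitual lenses.

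The cost is SAP wording, one derived variable and one line in the Visit 1 list. Visits and sample size stay as they are. The restricted analysis uses fewer participants and is less precise, and the zero-error estimate relies on a roughly linear relation.
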